4 METHODOLOGY

- 4.3 Study Details and Procedures
- 683 **Study Design and Sampling**: This is a single arm, open-label Phase I, non-randomized study.
- Participants meeting the inclusion criteria will be sequentially enrolled.

685

681

- 686 **Study Population:** The study population will be up to 16 women 18 years or older living in
- Kisumu County in Kenya, in order to have 12 fully evaluable participants, our desired sample
- size. Fully evaluable participants are those who receive artesunate inserts for 5 consecutive days
- and undergo blood draws before and after receiving artesunate at all the timepoints per study
- 690 protocol. Enrollment will stop once data from 12 fully evaluable participants are obtained. No
- more than 16 participants will be enrolled.

692 693

694

695

696

697

698

699 700

Inclusion Criteria

- 1. Age 18 years or older
- 2. Negative pregnancy test at screening
- 3. Weight ≥50 Kg at study entry*
- 4. Willingness to use contraception (hormonal or barrier) during the 5-day study dosing phase if of childbearing age (less than 50 years of age)
- 5. Ability and willingness to provide informed consent
- 6. Plan to reside in the study location during the study period
- *Justification for weight criteria: A minimum body weight of 50Kg will meet the planned artesunate dosing of ≤ 4 mg/Kg for which excellent safety data is available.

702 703 704

705

706

707

708

709

710

711

712

713

701

Exclusion Criteria

- 1. Current pregnancy or breastfeeding status
- 2. History of total hysterectomy
- 3. Known allergy to Artesunate
- 4. Have a medical comorbidity that in the opinion of the investigator would interfere with study participation
- 5. Currently receiving artemisinin-based agents for malaria treatment or completed artemisinin-based treatment within the previous 3 days.*
- Male at birth
 - 7. Current use of efavirenz antiretroviral therapy
- 714 8. Positive malaria antigen test at screening
- *Based on dihydroartesunate (artesunate's active metabolite) half-life of between 0.5-1.5 hours²⁹
- 717 **Study Location:** The study will be carried out at the Lumumba Sub-County Hospital and at the Victoria Biomedical Research Institute in Kisumu, Kenya.
- Recruitment: Participants will be recruited from among women in the general population within the vicinity of the study location, including within health facilities in Kisumu County in Kenya.

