Management and reporting of adverse events: Based on the prior Phase I study of intravaginal artesunate at this dosage and frequency, self-limited grade 1 (mild) AEs are expected, and grade II (moderate) AEs will be few, while grade 3 or worse AEs are not expected. In this study, AEs will be elicited and recorded in the participant study records at each study visit. All local AEs will be considered causally related to administration of the study drug. Causality of all other AEs will be assessed individually. Participants with grade I or II AEs will be followed until resolution of AEs. Grade II AEs will be managed symptomatically. Vaginal infections including yeast infections will be treated with oral medications during the dosing phase. Significant local inflammation, if any, will be treated with oral analgesics. Local infection or ulceration, which are unexpected, will be treated with routine wound care and antibiotics as necessary. Participants found to have any grade 3 or higher AEs will be instructed to stop study drug use, and the Data and Safety and Monitoring Board (DSMC) notified within 5 business days of the PI become aware. Participants will not resume study drug use until the DSMC decides that the AE is not related to the study drug.

871 872 873

874

Outcomes of AEs will be assessed as: 1) Recovered, 2) Recovered with sequelae, 3) Ongoing at participant end-of-study visit, 4) Died, 5) Unknown.

Pregnancies detected during the study (after first use of Artesunate (Visit 1) through Visit 5) will be recorded as SAEs. The participant will be referred for prenatal care, preferably to a provider who is experienced in reproductive toxicity for further evaluation and counseling. The Investigator will attempt to follow the participant until completion of the pregnancy and document the outcome of the pregnancy (either normal or abnormal outcome) and report the condition of the fetus or newborn to the Study Coordinator, if possible. If the outcome of the pregnancy was abnormal (e.g., spontaneous or therapeutic abortion), the Investigator will report the abnormal outcome as an AE.

For all adverse events reported or observed, the information should be recorded in the Case Report Forms for that participant. This will include a full description of the event, its seriousness, its severity or toxicity grade (intensity), the relationship to the study drug, and the treatment, outcome, and sequelae of the event.

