Any serious or unexpected event, which occurs to any participant in the course of her treatment on this study or within 30 days following cessation of treatment, must be reported immediately to the Study Coordinator by telephone at [name] or within 24 hours of the investigator learning of its occurrence. The immediate reports should be followed promptly by detailed, written reports. The Study Coordinator will then inform the Principal Investigator of the Adverse Event The PI is responsible for reporting AEs.Copies of these reports should be sent to:

• IRB

Reporting is required of all unanticipated problems to the UNC IRB, including those which may occur after the participant has completed or has withdrawn from the study, including after study closure.

Funding Source (if appropriate)

Unanticipated problems as defined by the UNC IRB:

903 Un 904 (U

Unanticipated problems involving risks to participants or others" or "Unanticipated Problem" (UP) refers to any incident, experience, or outcome that:

 is unexpected (in terms of nature, severity, or frequency) given (a) the research procedures that are described in the protocol-related documents, such as the IRB-approved research protocol and informed consent document; and (b) the characteristics of the participant population being studied;
 is related or possibly related to a participant's participation in the research; and

 suggests that the research places participants or others at a greater risk of harm (including physical, psychological, economic, or social harm) related to the research than was previously known or recognized.

Unanticipated Problems that are serious adverse events should be reported to the UNC IRB within one (1) week of the investigator becoming aware of the event. Any other Unanticipated Problem should be reported to the UNC IRB within two (2) weeks of the investigator becoming aware of the problem. If the Unanticipated Problem Report cannot be completed in its entirety within the required time period, a preliminary report should be submitted. The Unanticipated Problem Report should be amended once the event is resolved and/or more information becomes available.

PI: [name] Version 1.0

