All individual AE and IND Safety Reports shall be maintained by the Principal Investigator. For those events that are not reportable to the UNC IRB, a summary (i.e., not individual reports) of all adverse events that have occurred within the last approval period should be submitted to the UNC and Kenya IRB's at the time of continuing review.

Reports from a Data and Safety Monitoring Committee, (DSMC), or other independent safety monitoring group should be provided to the UNC and Kenya IRBs on a regular basis, generally at least as often as the study undergoes continuing review. Reports should include findings from adverse event reports and recommendations derived from data and safety monitoring.

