Biosafety: To ensure the safety of our research staff, study participants, and the surrounding community, we will follow the biosafety level 2 (BSL-2) standard as per the Kenyan Laboratory Biosafety and Biosecurity Policy Guidelines and Kenya National Guidelines for Safe Management of Health Care Waste. This standard is designed to reduce or eliminate exposure of laboratory workers, other persons, and the outside environment to potentially hazardous or detrimental materials. The study drug (artesunate) is a well-characterized drug that has been extensively studied and is not known to cause disease in healthy individuals. The biological material handled, and biological waste generated during the study are moderate-risk infectious agents and pose a moderate individual risk and low community risk of exposure. By following these guidelines, we can ensure that all our procedures are conducted safely, and that medical waste is disposed of properly.

Monitoring/Data and Safety Monitoring: The Principal Investigator will provide continuous monitoring of participant safety in this trial with periodic reporting to the Data and Safety Monitoring Committee (DSMC). Meetings/teleconferences will be held at a frequency dependent on study accrual. These meetings will include the investigators as well as study coordinators, data coordinators, regulatory associates, and any other relevant personnel the principal investigators may deem appropriate. At these meetings, the research team will discuss all issues relevant to study progress, including enrollment, safety, regulatory, data collection, etc.

The team will produce summaries or minutes of these meetings. These summaries will be available for inspection when requested by any of the regulatory bodies charged with the safety of human participants and the integrity of data including, but not limited to, the oversight of Office of Human Research Ethics Biomedical IRB.

The UNC PI will be responsible for submitting the following information for review: 1) safety and accrual data including the number of participants treated; 2) significant developments reported in the literature that may affect the safety of participants or the ethics of the study; 3) preliminary response data; and 4) summaries of team meetings that have occurred since the last report. Findings of the DSMC review will be disseminated by memo to the UNC PI, the UNC IRB, and all Kenya regulatory bodies governing the study.

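### After a drug-related grade 3 or higher adverse event the written response covers only the affected woman, so about two others may start before the DSMC must be told

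*Combined protocol and SAP*

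**What the plan says.** Section 4.3 Adverse Event Reporting, under management and reporting of adverse events, contains the plan's only dosing stop tied to adverse event grade. It applies to the participant with the grade 3 or higher event. The DSMC is to be "notified within 5 business days of the PI become aware", and "Participants will not resume study drug use until the DSMC decides that the AE is not related to the study drug". The same paragraph sets a causality default: "All local AEs will be considered causally related to administration of the study drug". Other events are assessed one by one.

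Oversight beyond the individual is described elsewhere:

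- **Reporting (4.3).** Serious or unexpected events go to the study coordinator "within 24 hours of the investigator learning of its occurrence", and copies of the reports go to the IRB. Unanticipated Problems reach the UNC IRB within one week if they are serious adverse events, and otherwise within two weeks. Of the DSMC's reports to the IRBs the plan says: "Reports should include findings from adverse event reports and recommendations derived from data and safety monitoring".
- **Monitoring (under 4.4 Specimen collection).** The PI monitors continuously and submits "safety and accrual data including the number of participants treated". "Meetings/teleconferences will be held at a frequency dependent on study accrual". DSMC findings go by memo to the PI, the UNC IRB and the Kenyan regulators.
- **Removal of participants (same section).** The PI may remove a participant for safety reasons.
- **Section 6.1.** Investigators may depart from the protocol to remove an immediate hazard. The IRB, the FDA and other named bodies may discontinue the study. The DSMC is not on that list.

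The stated conditions for ending enrolment are numerical: 12 fully evaluable women, or 16 enrolled. Evaluability depends on an unbroken course: "Fully evaluable participants are those who receive artesunate inserts for 5 consecutive days".

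**The concern.** The DSMC's decision is attached to the question that matters least. A course is five daily inserts. If notice takes the permitted 5 business days, and the decision then takes a time that the plan does not set, the stopped woman's course would normally be over before any ruling on resumption. The live question after a drug-related severe event is whether the next volunteer should start the same regimen, and the plan ties nothing to it.

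The causality default sharpens this. A local grade 3 event counts as drug-related as soon as it is found, with no adjudication to wait for, yet dosing of other women continues unless someone chooses to intervene. Section 5.3 describes individual benefit as minimal, so volunteers lose little by a short wait and could be spared an avoidable exposure.

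**Working it through.** **1. The plan's own figure.** Section 4.5.1 expects 2 enrolments a week and 6-8 weeks of accrual. 12/2 = 6 and 16/2 = 8 weeks, so it reproduces.

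**2. Starts before the DSMC must be told.** 5 business days is about 7 calendar days; 7 × 2/7 = 2 further women. If a decision takes another 1-2 weeks (assumed, since no deadline is stated), the total is 4-6. Others in mid-course at any moment: 2/7 per day × 4 days from first to last insert = 1.1.

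**3. How likely a triggering event is.** Section 1.2.2.1 reports no grade 3 or 4 events in the prior study. Taking 0 of the 28 women in its modified intention-to-treat set, the exact one-sided upper 95% bound is 1 − 0.05^(1/28) = 10.1%. This is only a rough guide. That study was dose-escalation, so fewer than 28 may have had this regimen, which would raise the bound. It also included women using three five-day cycles against one here, so it covers longer exposure than this trial.

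Let p be the assumed true rate per woman of a drug-related grade 3 or higher event, independent between women.

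| p | At least 1 in 12: 1 − (1 − p)^12 | Of 12, mean still to start when the first event is known, given one occurs | Same, unconditional |
|---|---|---|---|
| 1% | 11% | 3.9 | 0.4 |
| 5% | 46% | 4.3 | 2.0 |
| 10% | 72% | 4.9 | 3.5 |

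The unconditional mean is the sum over k of max(12 − k − 2, 0) · p(1 − p)^(k−1), where k is the position of the first affected woman and two women have started after her. Dividing by 1 − (1 − p)^12 gives the conditional mean. Replacements are left out.

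**4. Size of the replacement effect.** If every event broke the five-day course and nothing else caused losses, mean enrolment to reach 12 evaluable (cap 16) is 12.1, 12.6 and 13.3: an extra 0.1, 0.6 and 1.3 women. A woman whose event appears after the fifth insert with all samples taken may still be evaluable, so the true effect is smaller.

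**5. Cost of a hold.** 24 hours plus 5 business days is 1 + 7 = 8 calendar days; 8 × 2/7 = 2.3 starts deferred. Coincidental local grade 3 events would also trigger it. With an assumed coincidental rate q = 2%, the rate per woman is r = 1 − (1 − p)(1 − q) = 2.98%, 6.9% and 11.8%.

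| p (with q = 2%) | At least 1 trigger in 12 | 3 or more triggers in 12 |
|---|---|---|
| 1% | 30% | 0.5% |
| 5% | 58% | 4.5% |
| 10% | 78% | 16% |

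**6. Room in the timetable.** The stated 3 months is about 13 weeks. 13 − (6 to 8) − 2 weeks of participation leaves 3-5 weeks, or 21-35 days. 21/8 = 2.6 and 35/8 = 4.4, so about 2-4 holds fit. This assumes that the 3 months covers participant visits only.

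**The case against.** The strongest reply is that the plan already has people able to act. The PI can remove a woman in mid-course for safety. The plan itself says that grade 3 or worse events are not expected, so a related one could well qualify as an Unanticipated Problem and reach the UNC IRB within one or two weeks; that body can end the study. DSMC memos go to the IRB and the Kenyan regulators, so its absence from the discontinuation list matters less than it seems. Pause rules may also sit in a DSMC charter that was not supplied. On this view the point is only a preference for an automatic rule.

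Much of this stands, and it rules out stronger readings:

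- A reader might infer that the trial lacks trial-level safety oversight, or that the DSMC cannot influence continuation. The documents do not support either.
- A reader might infer that replacement feeds a material number of extra volunteers into the regimen. Step 4 shows about 0.1 to 1.3 women, so it is a minor part.
- A reader might take the 10% scenario as a forecast. It is roughly the upper bound from zero events.

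The reply does not supply a trigger. A route of one to two weeks to the IRB is no faster than accrual of 2 women a week, the 24-hour report is addressed to the study coordinator with copies to the IRB, and in section 4.5.2 the grade 3 or higher proportion is reported with no threshold or action. Full compliance with the written notice period still allows about two new starts first.

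Two objections to the remedy also stand: a hold can upset visit windows, and women in mid-course still depend on the PI's judgement.

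**Conclusion.** The point holds as a gap that should be closed, not as a failure of oversight. In the supplied text, the response to a grade 3 or higher event reaches only the affected woman, DSMC notice may take as long as her course, and continuation for everyone else is the default. The direct consequence is about two further starts before the DSMC must be told. If an event occurs and is known after two later starts, a mean of about 4 to 5 of the 12 women are still to begin, and these are the ones a rule could protect.

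The absolute risk is probably low. The 1%, 5% and 10% event rates, the 2% coincidental rate and independence between women are assumptions. Confidence is medium, chiefly because a DSMC charter could already contain such a rule; if so, citing it in section 4.3 would be enough.

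**What to change.** In section 4.3, under management and reporting of adverse events, add that after any grade 3 or higher event that the PI judges drug-related, and after any local one (deemed related already):

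1. the DSMC is notified within 24 hours instead of 5 business days;
2. no further woman receives a first insert until the DSMC recommends continue, modify or stop, within a stated time such as 5 business days;
3. the PI documents, before the next insert, whether each woman in mid-course continues.

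In section 6.1, under study discontinuation, name the DSMC as a body that may pause the study.

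This is wording in two places and needs no new committee, but the DSMC must be able to answer in the stated time. Each hold lasts up to about 8 days and defers about two starts. Some screened women may need rescreening or rescheduling, because Visit 1 must fall within 14 days of screening and at least a week before expected menses. A coincidental local grade 3 event can trigger a hold needlessly. Step 3 leaves mid-course dosing to the PI, but makes the decision explicit, timed and recorded.

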- screening activities, participants will have a malaria antigen test to screen for subacute malaria
- infection. Those who test positive will be referred for treatment and considered screen failure.

747 748

749

750

751

752

753

754

755

756 757

758

Screening/enrollment visit activities:

- Confirm eligibility
- Obtain informed consent
- Assign unique participant ID number
- Study protocol counselling (introduce the study to the participant, explain all study activities and timing, length, expectations of the participant, demonstration of intravaginal *Artesunate* application using pelvic model, discussion of tampon use etc.)
- Perform limited physical and pelvic exam and colposcopy with digital imaging
- Collect locator information
- Urine pregnancy testing
- Review concomitant/prohibited medications
- Obtain basic demographic and clinical data

759 760 761

762

Visit 1: Visit 1 can occur on the same day or up to 14 days following the screening/enrollment visit. Visit 1 will be timed to be no less than 1 week before the participant's anticipated menstrual cycle, for menstruating participants.

763764765

766

767 768

769 770

771

773

774

Visit 1 activities:

- Confirm eligibility
- Update locator information (if necessary)
- Review artesunate self-administration instructions and study protocol
- Review concomitant/prohibited medications
- Draw blood (~2.5ml) before artesunate self-administration
 - Artesunate self-administration using applicator, followed by tampon
- Observation for 30 minutes
 - Provide transport reimbursement
 - Schedule Visits 2

775 776

Visit 2-4: Visits 2, 3 and 4 must occur sequentially (within 24 hours) of each other. Attempts will be made to start visits at approximately the same time each day.

777 778 779

780

781

784

Visit 2-4 activities:

- Update locator information (if necessary)
- Review and record adverse events using standardized questionnaire
- Perform pelvic exam as needed based on AEs described (pelvic exam for suspected grade II or worse AEs)
 - Review concomitant/prohibited medications

- Artesunate self-administration using applicator, followed by tampon insertion
- Observation for 30 minutes
 - Provide transport reimbursement
 - Schedule subsequent visit

789 790

785

786

787

788

Visit 5: Visit 5 will occur one day (~24 hours) after Visit 4. Attempts will be made to start visits at the same time each day.

791 792 793

794

795

796 797

798

799

800 801

Visit 5 activities:

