- 1219 (CTCAE 5.0) and the Division of AIDS Female Genital Adverse Events Grading Table
- 1220 Statistical Analysis: The counts of adverse events for each participant will be tabulated by
- severity (grades 1-5). The proportion of participants with a severe AE (grade 3 or higher) will
- be reported along the exact (Clopper-Pearson) one-sided upper 95% confidence bounds. The
- proportion of participants who report a severe AE (if any) will also be reported, along with an exact one-sided upper 95% confidence bound.

1225 1226 1227 - The at-risk period for safety will begin at study visit 1 (first artesunate use) and will continue through study visit 6 (4-10 days after last artesunate use). Safety data will be reported for all participants who start artesunate use.

- Pharmacokinetic analysis: Conventional pharmacokinetic parameters AUC (0, infinity), halflife, apparent clearance, volume of distribution, maximum plasma concentration (Cmax), time to
- 1232 Cmax will be determined from the plasma concentration-time data using noncompartmental
- analysis. 35,76 Peak plasma concentration (Cmax) and time to reach peak concentration (Tmax) for
- artesunate and DHA will be the observed values. The AUC of AS will be calculated by linear
- trapezoidal summation with extrapolation to infinity, and AUC time curve will start from drug
- administration to the last quantifiable observation. All parameters will be calculated using time
- in hours after the first drug administration. With respect to DHA, AUC will be calculated to the
- last drug measurable time point. The elimination rate constant (beta) will be calculated from the
- slope of the terminal phase of the log concentration-time profile, and the elimination half-life

- 1240 (t1/2) calculated from the ratio of ln 2/beta. Other PK parameters will be calculated using
- standard model-independent formulae.³⁹ The estimates of PK parameters for DHA will assume
- 1242 complete conversion of AS to DHA as reported previously.³⁵ Data will be plotted graphically
- and analyzed using statistical software. Data will be presented as mean with standard deviation
- 1244 (SD).
- 1245 **4.6 Community Engagement Plan**
- 1246 The target population will be sensitized about the study through talks in public forums including
- health facilities within Kisumu County where the study will be done.
- 1248 4.7 Study Limitations, Risks and Mitigation of Risks

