5.4 Potential Harms and Minimization of Harms

- 1315 Potential risks to participants include risk of adverse events (AEs) following artesunate pessary
- 1316 use, risks associated with venipuncture include slight pain during the entry of the needle into the
- skin, very rarely possible dizziness, and syncope, risk of breach of confidentiality from study 1317
- 1318 participation, and theoretical (but minimal) risk of developing artemisinin resistance for malaria
- 1319 treatment following intravaginal use. The strategy to minimize these risks as discussed below:

1320

- 1321 Risk of adverse events from artesunate pessary use: Risk of adverse events are expected to be 1322 minimal based on the excellent safety profile of intravaginal artesunate at the planned dose and
- 1323 frequency in a U.S Phase I study. In that trial, of 37 drug-related AEs reported, 34 (92%) were
- 1324 grade 1 (mild), and only 3 (8%) were grade II, including 2 cases of vaginal yeast infection and 1

CONFIDENTIAL

PI: [name] UNIVERSITY OF NORTH CAROLINA April 25, 2023 Version 1.0

1325 case of non-infective cystitis. In this study, there were no grade 3 or higher AEs and no 1326 intolerable side effects that led to study withdrawal. As such, we expect risks related to AEs in 1327 this trial to similarly be minimal. There are no data on safety of intravaginal artesunate in 1328 pregnancy. Pregnancy is an exclusion criterion in this study. All participants will have pregnancy 1329 testing done at study entry to rule out pregnancy and will be required to use contraception if of 1330 childbearing age during the 5-day dosing phase.

1331 1332

1333

1334

1335

Risk associated with venipuncture: Participant monitoring, aseptic technique, including sterile disposable blood collection apparatus and adherence to standard medical precautions will reduce any risks associated with venipuncture to a minimum. The amount of blood to be taken for sampling will not be harmful to the participant's health, as it is significantly less (<1/10th) the volume of a normal blood donation.

1336 1337 1338

1339

1340

1341

1342

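### The pregnancy recording rule closes at Visit 5 (Day 5), before a conception during dosing is likely to be detectable, so recording and outcome follow-up of such pregnancies are not assured

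*Combined protocol and SAP*

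**What the plan says.** The pregnancy rule is in section 4.3 (Adverse Event Reporting), under management and reporting of adverse events: "Pregnancies detected during the study (after first use of Artesunate (Visit 1) through Visit 5) will be recorded as SAEs". The provisions that follow, referral for prenatal care and "The Investigator will attempt to follow the participant until completion of the pregnancy", apply to the pregnancies defined there.

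Section 4.2 fixes the timing: "Visit 1 will be timed to be no less than 1 week before the participant's anticipated menstrual cycle, for menstruating participants". Dosing is daily, and "Visit 5 will occur one day (~24 hours) after Visit 4", which makes Visit 5 Day 5. Visit 6, the last planned contact, comes 4-10 days later.

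Two other safety windows are longer:
- Section 4.3 also covers any serious or unexpected event during treatment or "within 30 days following cessation of treatment, must be reported immediately to the Study Coordinator".
- In section 4.5.2 the at-risk period for safety starts at first use and "will continue through study visit 6 (4-10 days after last artesunate use").

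Section 5.4 explains why pregnancy matters here: "There are no data on safety of intravaginal artesunate in" pregnancy. Contraception is an entry requirement for the dosing phase only.

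**The concern.** Pregnancy shows itself later than most events this trial looks for, yet it has the shortest recording window of the three. The rule's evident purpose is to learn the outcome of pregnancies exposed to a product with no pregnancy data by this route. A woman who conceives during the five dosing days is exposed, but her pregnancy would ordinarily become apparent only after Visit 5. She would then fall outside the only provision that makes a pregnancy a recorded SAE and starts follow-up to outcome. At stake is the completeness of the safety record, and whether an exposed woman enters the follow-up that the protocol intends for her.

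**Working it through.** The plan gives no figure to reproduce, so the check is day arithmetic.

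**Inputs from the protocol.** Visit 1 = Day 1; Visit 5 = Day 5; Visit 6 = Day 5 + 4 to Day 5 + 10 = Days 9-15; 30 days after the last insert = Day 5 + 30 = Day 35. Expected menses fall on Day 1 + g, with g at least 7 and no upper limit stated.

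**Assumed input.** L is the number of days from conception to a positive urine test. The documents do not give it, so it is varied from 4 to 14.

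**Step 1: missed period.** At the minimum g = 7, menses are due on Day 8, which is 8 − 5 = 3 days after Visit 5. With g = 10 or 14 the gap is 6 or 10 days. No menstruating participant on this schedule can have missed a period by Visit 5. This step needs no outside figure.

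**Step 2: urine test.** A conception on Day c (1 to 5) is 5 − c days old at Visit 5, so 0-4 days. It is detectable by Day d if c + L ≤ d. Conception days detectable by each date:

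| L (days, assumed) | Day 5 (Visit 5) | Day 9 (earliest Visit 6) | Day 15 (latest Visit 6) | Day 35 |
|---|---|---|---|---|
| 4 | 1 only | 1-5 | 1-5 | 1-5 |
| 5 | none | 1-4 | 1-5 | 1-5 |
| 6 | none | 1-3 | 1-5 | 1-5 |
| 8 | none | 1 only | 1-5 | 1-5 |
| 10 | none | none | 1-5 | 1-5 |
| 12 | none | none | 1-3 | 1-5 |
| 14 | none | none | 1 only | 1-5 |

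Any L above 4 days leaves the Visit 5 window empty of dosing-phase conceptions. A limit at Visit 6 would be only a partial remedy. A limit at Day 35 covers every case examined, since the latest detection date is Day 5 + 14 = Day 19.

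**Step 3: dependence on the test schedule.** The schema in section 2.4 lists urine tests at screening and at each of Visits 1-5. The Schedule of Events marks screening only. Step 2 assumes a test on Day 5, the more favourable case, so the result holds under either schedule.

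**Step 4: the windows compared.** The pregnancy rule ends on Day 5, the at-risk period on Days 9-15 (4-10 days later), and the serious or unexpected event window on Day 35 (30 days later).

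**Step 5: do the longer windows pick up pregnancy?** The SAE definition in section 4.3 covers congenital anomaly but not pregnancy itself, which becomes an SAE only through the rule ending at Visit 5. Visit 6 includes an adverse event questionnaire, but no listed pregnancy test or pregnancy question, and the symptoms named for elicitation do not include menses. After Visit 6 the off-study criteria end follow-up.

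**The case against.** A reader might infer that exposed pregnancies will go unrecorded, or that the rule cannot capture any. The documents do not support either reading.

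- **Other routes exist.** Adverse events are reviewed at Visit 6, serious or unexpected events are reportable for 30 days, the investigator may class an important medical event as serious, and unanticipated problems are reportable even after study closure. A later pregnancy that becomes known could be recorded by one of these. What clearly ends at Visit 5 is automatic SAE status and the referral and outcome follow-up attached to it.
- **The rule is not empty.** Screening may precede Visit 1 by up to 14 days. A pregnancy conceived before Day 1 is also exposed, and can be detected by Visit 5 if the schema's tests are done.
- **Visit timing alone proves less than it seems.** It rules out a missed period by Day 5, and only in menstruating participants. For urine testing the conclusion needs a latency from outside the documents, although any value above 4 days is enough.
- **A plain 30-day window would over-capture.** With L of 10-14 days, a window to Day 35 would take in conceptions as late as Day 35 − 14 = Day 21 to Day 35 − 10 = Day 25. Contraception is required only during dosing and the protocol expects rapid elimination, so most conceptions from Day 6 on would be expected to be unexposed.
- **Scale is small.** There are at most 16 women, with a negative screening test and contraception during dosing, and no pregnancy endpoint is planned.
- **Some material is not available.** The consent pages and the participant study card might already tell women to report a later pregnancy.

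All of these stand as limits on the point. None explains why the pregnancy rule stops at Visit 5, and none makes recording or outcome follow-up of a dosing-phase conception assured.

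**Conclusion.** The concern holds in a limited form. The pregnancy rule ends at least 3 days before menses can be due in menstruating participants, when a dosing-phase conception is 0-4 days old. For any urine-test latency above 4 days, which is an assumption, such a conception is not detectable inside the window. The rule is also out of step with the protocol's two longer safety windows, and those give a possible but unassured route to a record. The failing lies in a stated rule that serves its purpose poorly, and it is worth correcting. The likely number of events is very small, and neither the PK endpoints nor the planned adverse event tabulation is put in doubt.

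**What to change.** 1. In section 4.3, redefine the pregnancies covered by exposure and by when they become known: any pregnancy with estimated conception on or before the last dosing day (or where this cannot be excluded) that becomes known to the study team by 30 days after the last insert is recorded and followed to outcome. This loses nothing now covered, because a pregnancy detected by Day 5 was conceived by Day 5. It also avoids making every conception up to Day 35 an SAE.
2. Say in the same place how this rule relates to the 30-day reporting window in section 4.3 and the at-risk period in section 4.5.2, and that outcome follow-up continues despite the off-study criteria. Leave the section 4.5.2 analysis period at Visit 6; an analysis period and a reporting duty may differ.
3. Add a question on menses and known pregnancy to the existing Visit 6 questionnaire. It will not settle every case: menses are due by a Day 9 visit only if g ≤ 8, and by a Day 15 visit only if g ≤ 14.
4. Ask participants to report a later pregnancy, if the consent form or study card does not already do so.
5. Reconcile the pregnancy-test entries in the section 2.4 schema and the Schedule of Events.

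The cost is protocol wording, one question on an existing form and one instruction to participants, with perhaps an occasional extra report and outcome follow-up. Capture after Visit 6 would still rest on self-report, because no contact is planned between Visit 6 and Day 35.
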